5.2. Demographic and Other Baseline Characteristics

Demographic and baseline characteristics will be tabulated using descriptive statistics by treatment group and overall. Tables will be produced for the following analysis sets: ITT, Safety, mITT, Month 12 PP and Month 24 PP (as appropriate), PK, PD, and Genotyping. The following variables will be included in the tables:

The demographic data are:

- Age at screening (years) and in categories
 - < 65
 - 65-<75
 - 75-<85
 - ≥ 85
- Sex
- Race
- Ethnicity
- Geographic Region (United States vs. Rest of World)
- Country
- Weight (kg) at baseline
- Height (cm) at baseline
- Body Mass Index (kg/m^2)
- Tobacco use status (ever, never)

Baseline characteristics will be summarized for both study eye and fellow eye whenever applicable. Baseline characteristics include:

- Study eye laterality (OD, OS)
- Study eye status (better-seeing eye vs. worse-seeing eye, based on NL-BCVA – in the case of ties, study eye status will be classified as the better-seeing eye)
- GA lesion size (mm^2) (assessed by FAF)
- GA lesion size in categories, determined by reading center (as randomized status and actual status):
 - < 7.5 mm^2
 - $\geq 7.5 \text{ mm}^2$
- GA lesion size categories (approximately tertiles based on APL2-303/304 combined data*) – study eye only
- Square root GA lesion size (mm)

- GA lesion location (subfoveal involvement vs. non-subfoveal involvement) (assessed by FAF)
- GA focality (unifocal vs. multifocal) (assessed by FAF)
- Number of areas of atrophy (none, 1, 2-5, 6-10, 11-20, >20, cannot be determined) (assessed from FAF)
- Presence of double-layer sign (DLS) (assessed by SD-OCT)
- Central subfield thickness (CST) (assessed by SD-OCT)
- Presence of macular neovascularization (MNV) (i.e., subclinical CNV) (assessed by Optical Coherence Tomography Angiography (OCT-A))
- Presence of pseudodrusen (assessed by near-infrared reflectance imaging)
- Number of intermediate/large drusen (0-5, 6-10, 11-20, and >20) (assessed by color fundus photography)
- NL-BCVA in ETDRS letters
- NL-BCVA categories (≥ 70 , ≥ 60 - < 70 , ≥ 35 - < 60 , < 35 ETDRS letters)
- NL-BCVA (< 60 vs. ≥ 60 ETDRS letters)
- LL-BCVA in ETDRS letters
- LL-BCVA categories (approximately tertiles based on APL2-303/304 combined data*) – study eye only
- IOP
- LLD in ETDRS letters
- LLD categories (< 20 vs. ≥ 20 ETDRS letters)
- LLD categories (approximately tertiles based on the APL2-303/304 combined data*) – study eye only
- NL-BCVA (< 60 vs. ≥ 60 ETDRS letters) and LLD (< 20 vs. ≥ 20 ETDRS letters) combinations
- Advanced AMD (fellow eye with: GA only, GA with CNV, CNV only, neither GA nor CNV)
- GA laterality (bilateral GA vs. study eye GA Only)
- Presence of CNV in fellow eye (as randomized and actual status (based on medical history))
- Lens status:
 - Phakic
 - Pseudophakic
- Reading speed assessment method

- Monocular and binocular maximum reading speed and critical print size (without adjustment for reading inaccuracy)
- Monocular maximum reading speed categories (<60, 60-<160, ≥160 words per minute (wpm))
- Monocular maximum reading speed categories (approximately tertiles based on APL2-303/304 combined data*) – study eye only
- Mean FRI Index score
- FRI Level (1,2,3,4)
- NEI VFQ-25 distance activity subscale score
- NEI VFQ-25 near activity subscale score
- NEI VFQ-25 driving subscale score
- Number of subjects currently driving at baseline
- NEI VFQ-25 composite score
- C3 Complement level
- C3 Complement level categories (tertiles of C3)
- Dry AMD status (iRORA, large drusen) (at Month 24 reporting only)

*Approximately tertiles will be specified consistently across the APL2-303/304 studies to the nearest clinically relevant level.

Baseline will be defined as the last available pre-treatment value taken on or before the first dose date of study drug. In the case a subject did not receive study drug in the ITT population, the last assessment prior to study exit will be used as baseline.

Conversions for height and BMI are as follows:

- Height (m) = Height (cm) x 0.01
- Body mass index (kg/m²) = Weight (kg) / [Height (m)]²

Demographics and baseline characteristics will also be listed for the ITT set.

5.3. Medical ocular and non-ocular History

Medical history will be coded using the Medical Dictionary for Regulatory Activities (MedDRA) dictionary version 23.1. Summaries will be presented by System Organ Class (SOC) and Preferred Term (PT) with counts and percentages by treatment group and overall. Each subject will be counted only once in each SOC or SOC/PT summary.

All ocular history will be summarized by SOC and PT with counts and percentages by treatment group and overall. The summaries will be produced separately for the study eye and the fellow eye. Any ocular condition associated with both eyes will be included in both summaries. Data listings of medical history and ocular history will be provided for the ITT set.

5.4. Prior and Concomitant Medications

Prior and concomitant medications will be coded using World Health Organization (WHO) Drug Dictionary version WHO Drug Global B3-format March 2021. Non-ocular medications will be presented for the ITT set by anatomical therapeutic class (ATC) level 2 (therapeutic main group) and preferred term with counts and percentages by treatment group and overall. A subject who took more than one medication will be counted only once if these medications belong to the same extended ATC classification. In addition, prior and concomitant ocular medications used in study eye will be summarized. Similar summaries will be provided for the ocular medications used in the fellow eye. Any ophthalmological medications (ATC2 = 'Ophthalmologicals') that are not assigned to an eye will be presented under both eyes in the ocular medications tables and will not be presented in the non-ocular medications tables.

Prior medications will be defined as those medications taken prior to the administration of study drug on Day 1. Concomitant medications will be defined as those medications taken following the first administration of study drug on Day 1. Hence medications started before study dosing and continuing into the treatment period are considered as both prior and concomitant medications.

Separate tables will be provided for prior and concomitant medications, respectively. A data listing of prior and concomitant medications, for both ocular and non-ocular medications will be provided for the ITT set.

5.5. Concomitant Procedures

Concomitant procedures will be coded using MedDRA version 23.1. Non-ocular procedures will be presented for the ITT set by preferred term with counts and percentages by treatment group and overall. A subject who had more than one procedure will be counted only once in the summary. In addition, concomitant ocular procedures in study eye will be summarized. Similar summaries will be provided for the ocular procedures used in the fellow eye.

Concomitant procedures will be defined as those procedures taken following the first administration of study drug on Day 1.

A data listing of all procedures, for both non-ocular and ocular procedures will be provided for the ITT set.

5.6. Exposure to Investigational Product

Exposure to the investigational product will be summarized for the ITT, mITT, and Safety sets. All analyses will be repeated for the first 12 months at both the Month 12 and final reporting as well as the full 24 months for the final reporting.

For the analysis of exposure data for the first 12 months, exposure data prior to the Month 12 visit will be summarized (i.e., the Month 12 injection will not be included in the summaries). For analyses of the full 24 months, all data will be summarized.

Injections in the fellow eye will be considered in the calculation of the duration of treatment but will otherwise be considered as a missed injection in the study eye for all other measures of exposure.

The total number of injections and total number of missed injections received in each treatment group will be summarized by treatment group to support per-injection based TEAE rates.

The following categories for reason for missed injections will be summarized by treatment group using frequency counts and percentages based on the total number of missed injections: COVID-19 (with a breakdown of COVID-19 reasons as collected in the electronic case report form (eCRF)) vs. non-COVID-19 reasons (any reasons other than eCRF documented COVID-19 reasons). The total number of injections per subject will be summarized by treatment group both as a continuous summary and as a frequency and percent summary. In addition, the following categories of the total number of injections per subject will be summarized by treatment group using frequency counts and percentages:

- First 12 months summaries
 - Monthly: 1-3, 4-6, 7-9, 10-12
 - EOM: 1-2, 3-5, 5-6
- Full 24 months summaries
 - Monthly: 1-3, 4-6, 7-9, 10-12, 13-15, 16-18, 19-21, 22-24
 - EOM: 1-2, 3-5, 5-6, 7-8, 9-10, 11-12

The number of subjects who received at least 75% of the planned injections for the study period (first 12 months or full 24 months) will be presented. For the first 12 months, subjects will be considered to have received 75% of the planned injections if they received at least 9 (out of 12) injections for the Monthly group or 5 at least (out of 6) injections for the EOM group. For the full 24 months, subjects will be considered to have received 75% of the planned injections if they received at least 18 (out of 24) injections for the Monthly group or at least 9 (out of 12) injections for the EOM group.

The number of subjects missing at least one injection will be summarized by treatment group. The number of missed injections per subject as well as a breakdown of the number of missed injections per subject due to COVID-19 reasons and due to non-COVID-19 reasons will be summarized by frequency and counts. Additionally, for the missed injections due to COVID-19, the subjects will be summarized by their maximum drug holiday in the following categories:

- No Consecutive Injections (Subjects who are missing an injection due to COVID-19 but not at 2 injection visits in a row)
- 2 Consecutive Injections
- 3 Consecutive Injections
- 4 or More Consecutive Injections

The number of missed injections is defined as the scheduled injections missed up to completion or discontinuation of study treatment.

Additionally, the duration of treatment and compliance will be summarized by treatment group.

Duration of treatment will be defined as

- Monthly group: (date of last injection +30) – date of first injection +1
- EOM group: (date of last injection +60) – date of first injection +1

The duration of treatment will be truncated to a subject's early termination date, month 12 cutoff date, or study completion date as appropriate.

Compliance (%) is defined as the number of injections administered divided by the number of scheduled injections up to completion or discontinuation of study treatment $\times 100$. Compliance will be summarized in the following groups: $<75\%$, $\geq 75\%$ to $<100\%$, 100% , and $>100\%$.

The number of subjects with scheduled IVT injection visits as well as the number of subjects receiving injections at each of the Months (1-24) will also be summarized by treatment group using frequency counts and percentages. For the EOM group, any injections given on the odd-numbered months will be presented as an unscheduled injection. In addition, to assess the impact of the COVID-19 pandemic on study drug exposure, the following summary will be provided by study visit:

- Number of missed IVT injection visits for study drug
- Number of missed IVT injection visits for study drug due to COVID-19 pandemic reasons
- Number of missed IVT injection visits for study drug due to non-COVID-19 pandemic reasons

Study drug administration will be listed by treatment group. In addition, a listing of total number of injections, duration of treatment, date and day of first and last dose and number of missed injections will be provided for the ITT set.

5.7. Protocol Deviations

Major and minor PDVs will be assessed by sponsor personnel following Protocol Deviation Management Plan.

A PDV is classified as major if there is the potential to significantly impact the completeness, accuracy, and/or reliability of the study data, or affect a subject's rights, safety, or well-being. All PDVs will be identified and finalized prior to the analysis of the first 12 months as well as the analysis of the full 24 month and documented.

In addition, a major PDV will be derived for any subjects who did not have a valid GA lesion area assessment for either Month 10 or 12 and who had not discontinued treatment prior to Month 12. The category for this deviation will be "Study Conduct/Procedures", the subcategory will be "Study Assessment", and the study specific category will be "No valid GA lesion area assessment for either Month 10 or Month 12".

PDVs will be presented for the ITT set by deviation category, subcategory, and study specific category with counts and percentages by treatment group and overall. In addition, similar summaries will be provided for major PDVs as well as for PDVs due to the COVID-19 pandemic.

All PDVs will be listed for the ITT set.

6. EFFICACY ANALYSES

Efficacy analysis including primary, key secondary, secondary, and exploratory analysis will be performed primarily using the mITT set, with subjects grouped according to the treatment assigned at randomization. Available data from all randomized subjects regardless of adherence to the protocol will be included in the efficacy analyses; this includes data from subjects who discontinued study drug early but continued with study assessments. All efficacy data will be listed for the ITT set.

Unless otherwise noted, hypothesis testing and estimation of treatment effects will be performed with a mixed effect model for repeated measure (MMRM) that includes data from all three treatment arms (PM, PEOM, and Sham). The Sham arm will represent the pool of the two sham treatment groups: SM and SEOM (i.e., the two sham arms will be pooled into a single “control” group). All hypothesis tests for efficacy endpoints will be two-sided.

Unless otherwise noted, analysis of efficacy endpoints (primary, key secondary, secondary, and exploratory) in the overall population will be adjusted for the following randomization stratification factors (actual status) and baseline covariates:

For primary efficacy endpoint

- Presence of CNV in the fellow eye (yes; no)
- Baseline GA lesion area ($< 7.5 \text{ mm}^2$ or $\geq 7.5 \text{ mm}^2$)

For key secondary, secondary, and exploratory endpoints

- Presence of CNV in the fellow eye (yes; no)
- Baseline GA lesion area ($< 7.5 \text{ mm}^2$ or $\geq 7.5 \text{ mm}^2$)
- Baseline value of the endpoint

Of note, the randomization stratification factors were assessed at the screening visit. In the event of a change in status in the GA lesion area between the screening visit and the baseline visit (i.e., GA lesion area $< 7.5 \text{ mm}^2$ at screening to $\geq 7.5 \text{ mm}^2$) then the baseline status will be used.

If a statistical model is not directly specified and if necessary, data will be analyzed with the following approaches:

- For continuous endpoints, the MMRM analysis described for the primary endpoint in Section 6.2.2.
- For categorical or ordinal variables, a Cochran Mantel Haenszel (CMH) test with the baseline category status, presence of CNV in the fellow eye (yes or no), and baseline GA lesion area ($< 7.5 \text{ mm}^2$ or $\geq 7.5 \text{ mm}^2$) as stratification factors.

6.1. Estimands

The primary scientific research question of this study is to assess the effect of pegcetacoplan compared with that of sham at Month 12 regarding the impact on GA lesion progression under-real-life conditions following the ITT principal.

The primary estimand in the study is defined through the following 5 attributes:

- **Population:** GA subjects defined through inclusion and exclusion criteria in the mITT population.
- **Treatment conditions:** The treatment regimen of interest in this study is PM, PEOM, and Sham.
- **Variable (or endpoint):** Change in total area of GA lesions in the study eye from baseline measured by FAF to Month 12.
- **Strategy for addressing intercurrent events:** See description of intercurrent events below.
- **Population-level summary:** Difference in mean change of GA lesion from baseline to Month 12 between pegcetacoplan and sham groups according to MMRM analysis.

The intercurrent events that will be considered are:

- Treatment discontinuation
- Lost to follow up
- Withdrawal from the study

The intercurrent events will be handled with a treatment policy strategy whereby any measured value will be used as is. Missing data resulting from these intercurrent events will be handled implicitly within the MMRM analysis that assumes missing at random.

The key secondary estimands will be defined and analyzed in the similar fashion as the primary estimand. The primary and key secondary estimands are summarized in [Table 2](#).

Table 2: Estimands of Study

Estimand	Definition	Attributes			
		A: Population	B: Variable (or endpoint)	C: Strategy for addressing intercurrent event	D: Population-level summary
		Main Analyses			
Primary	The effect of pegcetacoplan compared to sham at Month 12 in impact on GA progression	mITT	Change in the total area of GA lesions from baseline measured by FAF to Month 12	
 Treatment policy strategy for subjects who discontinue treatment, are lost to follow-up, or withdraw from the study 	Difference in mean change of GA lesion from baseline at Month 12 between pegcetacoplan and sham groups based on MMRM analysis
Key Secondary #1	The effects of pegcetacoplan compared to sham at Month 24 in impact on monocular maximum reading speed	mITT	Change in monocular maximum reading speed from baseline to Month 24	
 Treatment policy strategy for subjects who discontinue treatment, are lost to follow-up, or withdraw from the study 	Difference in mean change in monocular maximum reading speed from baseline at Month 24 between pegcetacoplan and Sham groups based on MMRM analysis
Key Secondary #2	The effects of pegcetacoplan compared to Sham at Month 24 in impact on mean FRI Index score	mITT	Change in mean FRI Index score from baseline to Month 24	
 Treatment policy strategy for subjects who discontinue treatment, are lost to follow-up, or withdraw from the study 	Difference in mean change in mean FRI Index score, from baseline at Month 24 between pegcetacoplan and sham groups based on MMRM analysis
Key Secondary #3	The effects of pegcetacoplan compared to Sham at Month 24 in impact on NL-BCVA score	mITT	Change in NL-BCVA score from baseline to Month 24	
 Treatment policy strategy for subjects who discontinue treatment, are lost to follow-up, or withdraw from the study 	Difference in mean change of NL-BCVA score from baseline at Month 24 between pegcetacoplan and sham groups based on MMRM analysis

6.2. Analyses of Primary Efficacy Endpoint

The primary efficacy endpoint is change from baseline to Month 12 in total area of GA lesion(s) in the study eye (in mm^2) based on FAF.

The hypotheses of interest and Type I error management for analyses of the primary endpoint are specified below and take precedence over that specified in the study protocol.

For the primary efficacy endpoint, sensitivity analyses (Section 6.2.3), supplementary analyses (Section 6.2.4), and subgroup analyses (Section 6.2.5) will be performed.

All analyses of the first 12 months will be performed at the Month 12 reporting as well as repeated at the final reporting. Unless otherwise specified, at the time of the final reporting, all analyses will be repeated using the data for the full 24 months.

6.2.1. Type I Error Management

The null hypotheses for the primary efficacy endpoint are the following:

- H_{1a} : There is no difference between PM and Sham in mean change from baseline to Month 12 in total area of GA lesion(s) in the study eye (in mm^2) based on FAF for the mITT set.
- H_{1b} : There is no difference between PEOM and Sham in mean change from baseline to Month 12 in total area of GA lesion(s) in the study eye (in mm^2) based on FAF for the mITT set.

For hypothesis testing of the primary efficacy endpoint, type I error will be controlled using a fixed sequencing approach by testing the two hypotheses (H_{1a} and H_{1b}) sequentially, beginning with H_{1b} . All hypothesis tests for the primary endpoint will be based on a two-sided alpha level of 0.05. The alpha will be adjusted in accordance with the protocol for the number of Data Monitoring Committee (DMC) unmasked reviews prior to the Month 12 analysis timepoint (i.e., 4 DMC unmasked reviews prior to Month 12: 2-sided alpha level = 0.0496). Testing for statistical significance proceeds to H_{1b} only if H_{1a} is statistically significant. The study will be considered positive if the first hypothesis (H_{1a}) is rejected.

6.2.2. Main Analysis of Primary Efficacy Endpoint

The primary endpoint will be analyzed in the mITT population with subjects grouped according to the treatment assigned at randomization.

A MMRM model will be used to analyze the primary endpoint. The analysis model will include treatment (PM, PEOM, sham), presence of choroidal neovascularization in the fellow eye at baseline (Yes, No) and baseline GA lesion area ($< 7.5 \text{ mm}^2$ or $\geq 7.5 \text{ mm}^2$) as fixed effects, time (study month, categorical) as a factor, the time \times treatment interaction term, and the baseline GA lesion area ($< 7.5 \text{ mm}^2$ or $\geq 7.5 \text{ mm}^2$) \times time interaction term. The least square [LS] mean change from baseline to Month 12 will be estimated from the model for each of three arms as well as the comparisons of each of the three arms to each other. For other time points of interest, LS mean change from baseline will be estimated and compared between treatments. For each estimated LS mean, the corresponding 95% CI will be presented based on the model. For the comparison of the LS means, the corresponding 95% CI and the 2-sided P-value along with the percentage difference (difference in LS means between the arms/the comparison group LS mean) will be

presented. A common unstructured covariance matrix will be used to model the within-subject errors, the sandwich estimator (Diggle, Liang, and Zeger 1994) will be used to estimate the standard errors of the fixed effects parameters, and the degrees of freedom will be partitioned into between-subject and within-subject portions. If there are convergence problems with the model, then a heterogeneous autoregressive (1) covariance matrix will be used. If convergence problems still exist, an autoregressive (1) covariance matrix will be used. The LS mean of the change from baseline in the total area of GA lesion(s) \pm the standard error will be plotted over time by treatment group.

The observed values for the total area of GA lesion(s) will be summarized by treatment group and visit for both the study and the fellow eye. Summaries will present the descriptive statistics for baseline, absolute values and change from baseline data by visit.

The mean change from baseline in the total area of GA lesion (s) in the study eye \pm the standard error will be plotted over time by treatment group.

All GA lesion (s) size data will be listed for the ITT set.

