6.2.5. Subgroup Analyses of Primary Efficacy Endpoint

Subgroup analyses will be performed to evaluate the consistency of the primary analysis results across subgroups defined by demographic and baseline characteristics. Analyses will be performed for the primary efficacy endpoint (change from baseline in total area of GA lesion(s) in the study eye at Month 12) for each of the following subgroups (as appropriate per actual subgroup sample size, levels with low sample size may be pooled to allow for an analysis to be conducted):

- Age Group (<75 years, 75 to <85 years, ≥85 years)
- Sex (male, female)
- Race (White, Black or African American, Asian, American Indian or Alaskan Native, Native Hawaiian or other Pacific Islander, multiple, unknown)
 - Note: If most subjects (e.g., >90%) are of a single race, this analysis will not be conducted.
- Geographic Region (United States vs Rest of World)
- Subgroups indicative of disease severity at baseline
 - Study eye baseline GA lesion size (<7.5 mm²; ≥7.5 mm²)
 - Study eye baseline GA lesion size categories (approximately tertiles based on APL2-303/304 combined data*)
 - Study eye baseline NL-BCVA categories (≥70, ≥60 - <70, ≥35 - <60, <35 ETDRS letters)
 - Study eye baseline NL-BCVA categories (<60 vs. ≥60 ETDRS letters)
 - Study eye baseline LL-BCVA categories (approximately tertiles based on APL2-303/304 combined data*)
 - Study eye baseline monocular maximum reading speed categories (approximately tertiles based on APL2-303/304 combined data*)
 - Baseline FRI Level (1,2,3,4)

- Subgroups associated with GA progression
 - Study eye baseline GA focality (multifocal, unifocal)
 - Study eye baseline GA lesion location (subfoveal involvement, without subfoveal involvement)
 - Baseline GA laterality (bilateral GA (with or without CNV in fellow eye) vs. Study eye GA Only)
 - Baseline CNV in fellow eye (Fellow eye CNV vs. No fellow eye CNV)
 - Study eye baseline LLD categories (<20 vs. \geq 20 ETDRS letters)
 - Study eye baseline LLD categories (approximately tertiles based on the APL2-303/304 combined data*)
 - Study eye baseline NL-BCVA (<60 vs. \geq 60 ETDRS letters) and LLD (<20 vs. \geq 20 ETDRS letters) combinations

*Approximately tertiles will be specified consistently across the APL2-303/304 studies to the nearest clinically relevant level.

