1.2.1 Mixed Effect Model for Repeated Measure

```
*-----  
* Read Analysis data  
*-----  
* In this example, repeated measures are available at  
* avisitn = 0.5 (baseline), 2 (Month 2),  
* 6 (Month 6), and 12 (Month 12)  
*-----;  
  
data ga;  
  set adam.adga;  
  if paramcd = 'SEGAORG' and  
  avisitn in (0.5, 2, 6, 12) and  
  ANL01FL = 'Y';  
  
  * trtan (actual treatment[number])  
  * 1 = APL-2 Monthly  
  * 2 = APL-2 Every Other Month  
  * 3 = pooled Sham group;  
  if trtan in (4,5) then trtan = 3;  
  
  * trt01 are trt02 are used in multiple imputation  
  * trt01 = 1 if Sham group  
  * trt02 = 1 if APL2 Monthly group  
  * trt01 = trt02 = 0 for APL2 EOM group;  
  if trtan = 3 then trt01= 1; else trt01 = 0;  
  if trtan = 1 then trt02= 1; else trt02 = 0;  
  
  * avisitc will be used in PROC TRANSPOSE;  
  if avisitn = 0.5 then avisitc = '00'; * Baseline;  
  if avisitn = 2 then avisitc = '02'; * Month 2;  
  if avisitn = 6 then avisitc = '06'; * Month 6;  
  if avisitn = 12 then avisitc= '12'; * Month 12;  
run;  
  
*****;  
*** MAIN ANALYSIS using MMRM ***;  
*****;  
  
proc mixed data=ga method=reml covtest empirical;  
  where avisitn NE 0.5; * exclude rows for baseline;  
  * cnv (CNV in the fellow eye)  
  * 0 = No  
  * 1 = Yes;  
  *base cat (baseline lesion size (<7.5 vs. ≥ 7.5));  
  class trtan cnv avisitn usubjid base_cat;  
  model chg = trtan cnv base_cat avisitn trtan*avisitn base_cat*avisitn  
  /cl;
```

```
repeated avisitn / subject=usubjid type=un r;  
lsmeans trtan*avisitn/pdiff cl e alpha=.05;  
ods output diffs= diff1 LSMeans= LSMean1;  
run;
```

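### The primary MMRM lets the lesion-size factor vary over visits but holds fellow-eye CNV constant, and it leaves out baseline factors the SAP lists as associated with GA progression; this is unused precision, not bias.

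*SAP*

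**What the plan says.** SAP section 6 states that the efficacy analyses "will be adjusted for the following randomization stratification factors (actual status) and baseline covariates". For the primary endpoint the list has two entries: fellow-eye CNV and the lesion-area category split at 7.5 mm². SAP 6.2.2 builds the model from these: "The analysis model will include treatment (PM, PEOM, sham), presence of choroidal neovascularization in the fellow eye at baseline (Yes, No" and then lesion-area category, categorical month, month by treatment, and lesion-area category by month. The sample code in SAP Appendix 1.2.1 agrees: "model chg = trtan cnv base_cat avisitn trtan*avisitn base_cat*avisitn". Neither place has a CNV-by-month term.

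SAP 6.2.5 has a group headed "Subgroups associated with GA progression". It includes "Study eye baseline GA focality (multifocal, unifocal"), "Study eye baseline GA lesion location (subfoveal involvement, without subfoveal involvement") and "Baseline GA laterality (bilateral GA (with or without CNV in fellow eye) vs. Study eye GA Only"), together with fellow-eye CNV and low luminance deficit. SAP 5.2 lists all of these among the baseline characteristics. Under 6.2.5 they serve only to split the data into subsets, and nothing in 6.2.3 or 6.2.4 adds the omitted ones as covariates.

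The slope and piecewise models (SAP 6.2.4.3, code in Appendix 1.2.3) also cross the lesion-size category with time and leave CNV as a main effect.

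**The concern.** The response is change from baseline in a lesion that keeps growing. If fellow-eye CNV is related to growth, its effect on the change should be small at Month 2 and larger at Month 12. A single coefficient forces it to be equal at every visit. Under an unstructured covariance that coefficient is set mainly by the early visits, where variance is low, so Month 12 is hardly adjusted for a factor on which the trial stratifies. The lesion-size factor does not have this restriction. In the slope models a CNV main effect alone means that CNV status is assumed not to alter the growth rate at all.

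Focality, location and laterality are a simpler case: the SAP names them as related to progression, has them at baseline, and does not use them where they could reduce residual variance.

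PEOM versus sham is the comparison at stake. SAP Table 1 gives it 81.5% power at SD 1.5 mm², against 99.2% for PM. Under SAP 6.3.1, key secondary testing in this study needs both primary hypotheses rejected, on the pooled route and on the APL2-303-only route alike.

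**Working it through.** **Inputs from SAP 3.4 and 6.2.1.** Growth 1.70 (PEOM) and 2.13 (sham) mm²/year, so the difference is 0.43. SD 1.50, or 1.25 as the alternative. 200 per group. Two-sided alpha 0.0495 in the power table and 0.0496 in the testing text.

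**Reproducing the plan's figure.** Non-central t with 597 df and non-centrality 0.43 / (1.5 × √(2/200)) = 0.43 / 0.15 = 2.87. At alpha 0.0495 this gives 81.5%, as in the table. At alpha 0.0496 it is 81.6%.

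**How much a constant CNV term adjusts Month 12.** Assume linear growth, FAF at Months 2, 4, …, 12, Month 12 SD 1.5, and measurement-error SD e per image. Then V_ij = s²·t_i·t_j/144 + e²(1 + [i = j]), with s² = 2.25 − 2e². If the true CNV effect at month t is d·t/12, the generalised least squares estimate of a single constant effect, as a fraction of d, is (1′V⁻¹(t/12)) / (1′V⁻¹1).

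- e = 0.2: 2.1%
- e = 0.3: 4.8%
- e = 0.4: 8.5%

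At e = 0.2 the visit weights are 0.65, 0.46, 0.26, 0.07, −0.12 and −0.32, so the early visits dominate. The constant term recovers roughly 2% to 9% of the Month 12 effect.

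**Simulation of the MMRM-type model** (300 runs per scenario, unstructured covariance, sandwich SE, linear growth, CNV share 35%, CNV effect 0.3 mm² at Month 12; all assumed). Mean reported SE for PEOM minus sham at Month 12:

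| Model | No other prognostic factors | Three covariates explaining a further 6.8% |
|---|---|---|
| SAP form | 0.1496 | 0.1497 |
| CNV × visit | 0.1488 | 0.1489 |
| Covariates as main effects only | – | 0.1495 |
| CNV and covariates, each × visit | – | 0.1437 |

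CNV by visit lowers the reported SE by 0.5% (0.1488/0.1496). Covariates entered without a visit interaction gain almost nothing; crossed with visit they lower it by 4% (0.1437/0.1497).

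**Power for PEOM versus sham.** Residual SD = SD × √(1 − R²), alpha 0.0496. R² is the Month 12 variance explained beyond the present model, and it is an assumption.

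| Added R² | Power, SD 1.5 | Power, SD 1.25 | Equivalent n per arm, 200/(1 − R²) |
|---|---|---|---|
| 0 | 81.6% | 92.9% | 200 |
| 0.02 | 82.3% | 93.4% | 204 |
| 0.05 | 83.5% | 94.1% | 211 |
| 0.10 | 85.4% | 95.1% | 222 |

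**CNV by visit alone.** R² = p(1 − p)d²/2.25 for CNV share p and Month 12 growth difference d.

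- p = 0.35, d = 0.3: R² = 0.0091, a gain of about 0.4 points.
- p = 0.5, d = 0.5: R² = 0.0278, a gain of about 1.1 points.

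**The case against.** The SAP follows a stated rule: adjust for the stratification factors. The protocol model (12.7.1) likewise has no CNV-by-time term and none of the three omitted factors. Further prognostic covariates are optional. The 81.5% comes from a covariate-free one-way ANOVA, and SAP 3.4 itself expects the longitudinal model to do better. At SD 1.25, PEOM power is already 92.9%. PM has 99.2% even at SD 1.5, and SAP 6.2.1 calls the study positive on PM alone. The heading in 6.2.5 carries no effect size, and laterality is defined on the same fellow eye as CNV, so its independent contribution may be small.

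There are practical objections too. Subgroup analyses reuse the 6.2.2 model on subsets where the SAP already expects low counts, and 6.2.2 already needs fallbacks for non-convergence. APL2-304 shares the testing strategy, so a change in one study alone would be awkward.

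Most of this stands as a limit on size and as a condition on the fix. It does not explain why one stratification factor is crossed with visit and the other is not, nor why factors the SAP regards as related to progression are unused in the main analysis.

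Two stronger readings are tempting.

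- A reader might infer that the primary test is invalid. It is not. Randomization is stratified on CNV, the standard errors use the sandwich estimator, and omitting a baseline covariate does not bias the arm comparison. If anything, the reported SE is slightly too large.
- A reader might infer a material power loss from the CNV term alone. Reaching 84.0% needs, for example, a CNV share of 35% and a growth difference of 0.8 mm². That exceeds the assumed PM effect (2.13 − 1.47 = 0.66) and is 38% of assumed sham growth (0.8/2.13). Nothing in the documents supports it.

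**Conclusion.** The point holds as one of efficiency. The primary model adjusts Month 12 very little for fellow-eye CNV and not at all for three baseline factors that the SAP associates with progression.

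The gain cannot be derived from the documents, which give no R², no CNV share and no CNV growth difference. For an assumed added R² of 2% to 10%, PEOM power rises by about 0.8 to 3.8 points at SD 1.5, and by about 0.5 to 2.2 points at SD 1.25. CNV by visit alone is likely worth about one point or less. PM power is too high for this to matter. The finding that a constant term barely adjusts Month 12 rests on roughly linear growth and a measurement-error SD of 0.2 to 0.4 mm².

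The change is worth making because it is nearly free and aimed at the weaker primary comparison, not because the present analysis is wrong.

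**What to change.** Before unmasking:

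- Add `cnv*avisitn` to the model in SAP 6.2.2 and Appendix 1.2.1.
- Add `FCNVAT*avisitn` to the slope model, and also `FCNVAT*avisitnspl1` to the piecewise model, in 6.2.4.3 and Appendix 1.2.3.
- Prespecify focality (unifocal or multifocal), location (subfoveal or not, the two levels the SAP defines) and laterality (bilateral or study eye only) as covariates in the main analysis, each crossed with visit. Main effects alone would not help at Month 12.
- Add low luminance deficit on the same terms, or state why it is left out when the other factors in that list are included.
- Keep the current model as a sensitivity analysis.
- Allow the added terms to be dropped in small subgroups, and state how missing covariate values are handled.
- Add the new covariates to the imputation models. CNV needs no change there, because the sequential regressions already give it a separate coefficient at each visit.
- Align the specification with APL2-304.

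The cost is SAP wording, a few more model parameters, and a rule for missing covariate values. No new data and no extra patients are needed.
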